The objectives of this study are to assess cost-effectiveness of a Young Moms Program that incorporates a traditional Parents as Teachers home visiting parenting program to that of a hybrid virtual/home based Parents as Teachers program, against short-term outcomes, which in turn will serve as leading indicators of longer-term results. Specific outcomes are outlined in the measures section.

Methods and Measures

This is a community-engaged research collaboration between the non-profit Imprints Cares, the WFBMC Birth Center, and WFSOM. Because YMP is a tiered program model, services meet parents where they are through a “warm hand-off” approach that uses on one-on-one consultation and assessment-based interventions. The YMP is designed to address systemic barriers to the health and stability of young moms and their children such as the lack of coordination of service delivery or logistical barriers within the health system. The YMP also streamlines the referral pipeline, connecting

Protocol version:

Template updated 9.24.14

moms to evidence-based resources, and ensuring children complete all recommended assessments prior to kindergarten.

This research project is a pilot randomized controlled trial. We expect a total of 30 participants, 15 in each arm of the study. For inclusion into this study participants must be an immediately post-partum mother, between 14-21 years of age who will reside with her newborn. The mother must be referred from either the Birth Center at Wake Forest Baptist Health or from one of the Wake Forest Baptist Health PPC partner practices. Exclusion criteria include that newborn of participating mothers must be ≥ 35 weeks of gestation and not have an extended NICU stay. These populations are excluded because medically complex newborns and a prolonged separation during the intervention period will directly affect our outcome measures. Participants must speak English or Spanish given our parent educators and other group participants are limited to those languages. Males are excluded as participants, the intervention and many of the outcome measures are only applicable to female participants.

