Participants will be randomly assigned to one of the two variants of the Parents as Teacher home visitation model, traditional or hybrid. The study's research coordinator, who is not directly involved with the delivery of services, will manage the randomization and assignment process; all consented participants will be given a system-generated unique identifier, which cannot be linked to patient identity by anyone except the research coordinator. This information will be securely maintained by the research coordinator. The team will complement the treatment groups' data with population data extracted from WFBMC's Epic system. Analysts will use rigorous techniques (e.g, Propensity Score Matching) to create a matched control group.

Both formats and all interventions included in the study are the current models of care for our existing PAT/YMP services. The hybrid model was developed in 2020 in response to the need to move services virtually as home visitation was not allowed during COVID-19 lockdown.

Through the traditional PAT model, participants will be referred through a warm hand-off from the Birth Center or one of WFBH community pediatric centers to Imprints Cares. A PAT certified family educator will meet with the family focusing on a one-on-one consultation and assessment-based interventions. Participants in the traditional PAT model will receive two home visits a month and participate in monthly peer (group) connections throughout the study period.

In the hybrid PAT model, participants will be referred through a warm hand-off to Imprints Cares from the Birth Center or one of WFBH community pediatric centers. A PAT certified family educator will meet with the family focusing on a one-on-one consultation and assessment-based interventions. Study participants will begin receiving services by participating in the virtual "What You Do Matters" program, an evidence-based PAT curriculum. After completion of the virtual program, young moms will begin receiving once a month home visits and participate in monthly peer (group) connections.

Protocol version:

Template updated 9.24.14

By including two variants in this pilot project, the study team will assess the cost-effectiveness of the two approaches, against short-term outcomes, which in turn will serve as leading indicators of longer-term results. At the end of the official study period, participants will be eligible to continue in the program until the child's school entry into kindergarten.

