Both models will be staffed by qualified family educators that have been trained in the Parents as Teachers Foundational Curriculum, the Circle of Security model, and breastfeeding educator certification program. Imprints Cares also has a mental/behavioral health family educator on staff to address emergent mental/behavioral concerns as they arise. These approaches have been documented to nurture parental attachment and secure relationships^{xi}.

Outcome Measures

The team will use several published assessments:

Protective Factors Survey. The Protective Factors Survey (PFS) is a validated parent survey designed that assesses protective factors in five areas: family functioning/resiliency, social support, concrete support, nurturing and attachment, and knowledge of parenting/child development. The PFS will be implemented at week one, week six, and end of study, as it requires parent-child interactions for completion.

Ages and Stages Questionnaire 3rd edition. The Ages and Stages Questionnaire (ASQ 3) is a validated developmental screening designed for use by and with parents. The ASQ 3 screens for developmental milestones in communication, gross motor, fine motor, problem solving, and personal-social skills. The ASQ 3 will be implemented at the recommended intervals designed by its publisher (2, 4, and 6 months).

Ages and Stages Questionnaire: Social-Emotional 2nd edition. Similar to the ASQ 3, the Ages and Stages Questionnaire: Social-Emotional (ASQ:SE 2) is a validated screening of social and emotional behaviors. The ASQ:SE 2 will be implemented at the recommended intervals designed by its publisher (2, 4, and 6 months).

Patient Health Questionnaire. The Patient Health Questionnaire (PHQ 9) is a self-administered questionnaire that is validated for use in assessing the severity of depression. The PHQ 9 will be administered as a baseline assessment as well as an end-of-study assessment.

StimQ2-I. The StimQ2-I is a validated, interview-based assessment of home environments for use with infants ages five to 12 months. The StimQ2-I focuses on cognitive stimulation by the primary caregiver and contains several scales: Availability of Learning Materials, Reading-Verbal, Parental Involvement in Developmental Advance, and Parental Verbal Responsivity. The StimQ2-I will be implemented at the end of study, as it requires parent-child interactions for completion.

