In addition to these assessments, the team will use an intake questionnaire to capture parent demographic and health information as well as baseline knowledge about child development and parenting and a monthly questionnaire used to assess mother's status on continuance of secondary education, breastfeeding, and use of contraception. A monthly questionnaire, which will be developed for use in this study, also will assess infant developmental milestones.

Further, the team will access health information captured in WFBMC's Epic system, including completion of Well-Child Visits and recommended immunizations. A WFBMC study team member will extract data on participants as well as a matched control group. The study team will conclude the study with participant focus groups, to collect additional qualitative feedback and insights. Finally, the team will develop and implement Fidelity of Implementation (FOI) quality

Protocol version:

Template updated 9.24.14

assurance guidelines and checklists to capture the degree to which project services are delivered as expected. FOI scores will be used as a predictive variable with the goal of establishing a minimum service threshold for short-term outcomes.

Proposed Statistical Analyses

Descriptive Analyses. All data will be subject to descriptive analyses, including measures of central tendencies and frequency distributions, as appropriate for the type of data collected. Descriptive analyses will support our understanding of participant characteristics and equivalency of samples in the traditional and hybrid models.

Inferential Analyses. Inferential analyses, such as t-tests, multiple regression, and Analysis of Variance, will be conducted to test for change between baseline and end-of-study data collections with the PHQ 9, and the PFS. The PFS will be administered at service week one, service week six, and at the end-of-study to assess differences between the models at promoting protective and nurturing behaviors. Tests also will be used to assess differences between the models on maternal outcomes such as continuance of secondary education, breastfeeding, and use of contraception and child-focused outcomes such as STIMQ2-I, completion of Well Child Visits and immunizations. The study team will work with CTSI Biostatistical Support services to advise and guide the analytic approach.

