- Collection of ASQ and ASQ:SE data as recommended by the publisher (2, 4, 6m).
- Collection of end-of-study data (6 months after enrollment). In the final month of services, the team will collect the ASQ, ASQ:SE, PHQ 9, the PFS and the StimQ2-I.
- Collection of FOI checklist data. Project staff and supervisors will complete FOI checklists on a monthly basis. Each model will have its own checklist.
- WFBMC data extraction and compilation of analysis files. One of the WFBMC team members will work to securely extract health data for treatment and matched control group participants from the Epic system.

Human Subjects Protection

Subject Recruitment Methods

No additional PHI will be accessed or printed/transcribed above and beyond what is part of standard patient care and pre-defined job descriptions.

OB Home Visiting Staff

- 1) Our OB Home Visiting Nursing Staff as part of their standard workflow identify and visit all post-partum mothers that reside in Forsyth County, NC.
- 2) Of those, they will identify mothers that meet inclusion criteria for the study (14-21 years old, Spanish or English Speaking, will reside with their newborn upon discharge, and will follow up with a Wake Forest Baptist Health Pediatrician).
- 3) During their standard meeting, while the mother is still inpatient from her delivery, OB home visiting staff per their standard workflow will ask if the mother would like referral to Imprints Cares. If they identify a likely eligible participant, they will introduce study at that time, without promising the patient they are eligible. If the patient is interested in referral for either the study or services not provided as part of the study, the team will make a referral to Imprints Cares. The referral will indicate if the patient appears to be eligible for the study or not.

Imprints Cares

- 1) After referral from the PPC primary care physician or the OB Home Visiting Nursing Staff to the Imprints Cares program, intake staff will assess if new mothers meet criteria for participation in the study (14-21 years old, Spanish or English Speaking, will reside with their newborn upon discharge, and will follow up with a Wake Forest Baptist Health Pediatrician).

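### The only PHQ 9 analysis the plan names is a test for change over time; the baseline-adjusted difference between the randomized models should be stated as its main analysis

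*Combined protocol and SAP*

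**What the plan says.** All references are to the combined protocol and SAP.

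- **Design (Methods and Measures).** "Participants will be randomly assigned to one of the two variants of the Parents as Teacher home visitation model, traditional or hybrid". The size is given as "We expect a total of 30 participants, 15 in each arm of the study". Both arms receive Parents as Teachers (PAT).
- **Aim (Methods and Measures).** With two variants in the pilot, "the study team will assess the cost-effectiveness of the two approaches, against short-term outcomes".
- **PHQ 9 data.** Under Outcome Measures: "The PHQ 9 will be administered as a baseline assessment as well as an end-of-study assessment". The milestone list under Study Timeline places the first PHQ 9 at enrollment, and for the close of follow-up it says "In the final month of services, the team will collect the ASQ, ASQ:SE, PHQ 9, the PFS and the StimQ2-I".
- **PHQ 9 analysis (Inferential Analyses).** After giving t-tests, multiple regression and ANOVA as examples, the plan says these "will be conducted to test for change between baseline and end-of-study data collections with the PHQ 9, and the PFS". The next sentence gives the Protective Factors Survey (PFS) a between-model purpose. The one after begins "Tests also will be used to assess differences between the models on maternal outcomes such as continuance of secondary education" and goes on to breastfeeding, contraception and several child outcomes. Neither sentence names the PHQ 9. No model terms or covariates are given for any outcome.
- **Later advice (same paragraph).** "The study team will work with CTSI Biostatistical Support services to advise and guide the analytic approach".

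**The concern.** Three different analyses fit the wording for the PHQ 9: a paired test in each arm, a single paired test over all participants, or a comparison of change between the arms. Only the third uses the randomization.

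The first two have no comparator for whatever happens to depressive symptoms over the six months after birth. Both arms receive PAT, so neither serves as an untreated reference. The matched controls drawn from Epic do not fill the gap either, because no PHQ 9 is described for them. A significant fall in scores could then be credited to the program when it would have occurred anyway. Separate tests by arm carry a further risk: one arm may cross p<0.05 and the other not, and that pattern is easily mistaken for evidence that one model outperforms the other.

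**Working it through.** **Inputs from the documents.** 15 participants per arm; PHQ 9 at enrollment and at six months; two randomized arms. The documents give no alpha, power, SD, baseline-to-end correlation, expected shift or dropout, so there is no stated figure to reproduce.

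**Assumptions.** Two-sided 5% level; baseline-to-end correlation ρ of 0.3, 0.5 or 0.7; equal SDs at both times; all sizes in outcome SD units; a shared shift of 0.2 to 0.5 SD with no effect of either model; 12 completers per arm as a 20% loss case.

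**Step 1. Tests of change when neither model has an effect.** The standardized paired shift is d_z = shift / √(2(1 − ρ)). The two extremes are 0.2/√1.4 = 0.169 and 0.5/√0.6 = 0.645. Noncentral-t probabilities of p<0.05, for ρ = 0.3/0.5/0.7:

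| Test | n | Shift 0.2 SD | Shift 0.5 SD |
|---|---|---|---|
| Within one arm | 15 | 0.094 / 0.112 / 0.154 | 0.332 / 0.438 / 0.643 |
| Pooled | 30 | 0.146 / 0.185 / 0.277 | 0.609 / 0.754 / 0.927 |
| Within one arm | 12 | 0.084 / 0.097 / 0.130 | 0.267 / 0.353 / 0.532 |
| Pooled | 24 | 0.125 / 0.156 / 0.228 | 0.509 / 0.650 / 0.857 |

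**Step 2. Discordant arms.** In 100,000 simulated trials with 15 per arm and the same mean change in both arms, exactly one arm reached p<0.05 in 8% to 49% of trials for shifts of 0.3 to 0.8 SD, and in 9% with no shift. In a separate simulation of 40,000 trials with a shared 0.5 SD shift and no arm difference, the baseline-adjusted arm comparison rejected in 4.9% / 5.1% / 5.0%.

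**Step 3. Precision of the arm difference, 15 per arm.** The 95% CI half-widths are:

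- End scores only (28 df): 2.048 × √(2/15) = 0.75.
- Change scores (28 df): 0.748 × √(2(1 − ρ)) = 0.89 / 0.75 / 0.58.
- End score adjusted for enrollment score (ANCOVA, 27 df): 2.052 × √(2/15) × √(1 − ρ²) × √(1 + 1/26). The last factor allows for chance imbalance in the covariate. For ρ = 0.5: 0.749 × 0.866 × 1.019 = 0.66. For 0.3 / 0.5 / 0.7: 0.73 / 0.66 / 0.55.

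Relative to end scores only, the adjusted interval is 3% / 12% / 27% narrower. The difference detectable with 80% power is 1.03 / 0.94 / 0.77 SD adjusted, 1.06 with end scores, and 1.25 / 1.06 / 0.82 with change scores.

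**Step 4. With 12 completers per arm.** The adjusted half-width is 0.83 / 0.75 / 0.62 SD (21 df, factor 1 + 1/20), against 0.85 for end scores only. The ordering is unchanged.

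**The case against.** The strongest reply is that the plan is unspecific rather than wrong. Regression and ANOVA can carry a term for arm. The list of maternal outcomes to be compared between models is open-ended, and the PHQ 9 is a maternal outcome. The PFS shares the same sentence about change and is then given a between-model purpose, so the PHQ 9 may be meant the same way. Statistical support is to guide the details. This stands. A reader might infer that the plan excludes an arm comparison of the PHQ 9, or commits to uncontrolled before-and-after tests. The text supports neither inference. Equally, the probabilities in Steps 1 and 2 illustrate one possible reading under assumed inputs; they are not error rates of this plan.

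Two further replies have force. No passage makes the PHQ 9 primary, and the cost-effectiveness section does not mention it. That section also seeks benefits reachable within six months of service, so change over time has a descriptive use of its own. In addition, the gain from adjustment is modest at low correlation, and no option detects a small difference with 30 participants.

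None of this removes the need to choose. The three readings answer different questions, later advice does not fix the choice before data are seen, and the trial randomizes in order to compare the two models.

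**Conclusion.** The point holds as an unstated contrast for which a better analysis is available at almost no cost. The plan names only a test of change for the PHQ 9, leaves its form open, and does not write down the arm comparison that its design and planned data already allow.

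If the test is run within arm or pooled, it does not compare the models and can be significant with no effect of either: 9–64% of trials within an arm of 15 and 15–93% pooled over 30, given a shared shift of 0.2 to 0.5 SD and correlations of 0.3 to 0.7. If a comparison between arms is already intended, what remains is to say so and to adjust for the enrollment score. Adjustment narrows the interval by 3% to 27% relative to end scores alone.

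The adjusted result should be read as an estimate: differences below about 0.77 SD are not detectable with 80% power in any scenario examined. It compares hybrid with traditional delivery and cannot show whether PAT itself changes the PHQ 9. The change is worth making, but nothing here invalidates the trial.

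**What to change.** Add to Inferential Analyses:

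1. The main PHQ 9 analysis is a linear model of the end-of-study score on randomized arm and enrollment PHQ 9. The hybrid-minus-traditional difference is reported with its 95% CI, as an estimate.
2. Within-arm change is reported descriptively and not attributed to the program. The model estimates hybrid against traditional, not the effect of PAT.
3. The enrollment PHQ 9 is completed before assignment is known. The milestone list says only that it is collected at enrollment, and a covariate measured after assignment is known could be affected by it.

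A wording note on the PFS: Inferential Analyses speaks of its change from baseline, but the first PFS is taken in week one of services and is not among the baseline items in the milestone list. It should not be described as a pre-intervention baseline.

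The cost is a few sentences and one degree of freedom in the PHQ 9 model. No data items, visits or participants are added; item 3 may require fixing the order of two enrollment steps.

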Proposed Cost Effectiveness Study Design. One of the primary challenges of completing cost studies is fully accounting for all costs and benefits. Therefore, the study team will use this project period to identify the spectrum of costs associated with serving one young mother and her child. These data will be compiled to generate an average cost of service and establish outliers that exist when there are particularly risky or traumatic cases. In addition, the team will establish short-term benefits (achievable after six-months of services) along with the program implementation conditions necessary to achieve them. We will utilize the services of BERD and Q-Pro to assist in advising in areas of study design, data analysis, and data management.

Study Timeline

Study Milestone	M1	M2	M3	M4	M5	M6	M7	M8	M9	M10	M11	M12
Achieve IRB approval	•											
Enrollment of teen moms		•	•	•								
Baseline data collected		•	•	•								
Services delivered	•	•	•	•	•	•	•	•	•	•		
Week one data collected	•	•	•									
Week six data collected		•	•	•								
ASQ/ASQ-SE data collected (2,4, and 6m)			•	•	•	•	•	•	•	•	•	•
Monthly questionnaires and FOI checklists completed			•	•	•	•	•	•	•	•	•	
End of study data collected											•	•
Analysis and reporting completed												•

The project will track numerous milestones, including:

- Submission of IRB application and receipt of IRB approval. This milestone is critical as the project will not move forward without IRB approval.
- Enrollment of young moms by the project's four month. All participants will need to be enrolled by month four to ensure moms in both models can receive at least six months of home visitation services. In the traditional model, home visitation starts immediately upon

Protocol version:

Template updated 9.24.14

enrollment. In the hybrid model, home visitation starts at the completion of the six-week What You Do Matters virtual class.

- Collection of all baseline data. Baseline data will be collected at the time of enrollment and will consist of the enrollment form and the PHQ 9.
- Collection of week one and week six data. Data will be collected during the participant's first and sixth week (at the close of the What You Do Matters course) of services in both models (PFS).
- Collection of monthly questionnaires. Monthly questionnaires will be implemented with each participant, on a schedule developed by the family educator.

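### The PFS change test uses only the first and last of three scores, so a mother lost after week six drops out of it; a baseline-adjusted three-wave model would guard against selective loss

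*Combined protocol and SAP*

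**What the plan says.** The trial is small: "We expect a total of 30 participants, 15 in each arm of the study" (Methods and Measures). Outcome Measures sets the schedule: "The PFS will be implemented at week one, week six, and end of study". The Study Timeline places the last wave at six months: "Collection of end-of-study data (6 months after enrollment").

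Under Proposed Statistical Analyses, the Inferential Analyses paragraph gives an open list of methods, "Inferential analyses, such as t-tests, multiple regression, and Analysis of Variance, will be conducted", and their purpose: "to test for change between baseline and end-of-study data collections with the PHQ 9, and the PFS". The next sentence gives the three PFS waves a further purpose: "The PFS will be administered at service week one, service week six, and at the end-of-study to assess differences between the models". It names no method and no time point for that comparison.

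The baseline set in the Study Timeline leaves the PFS out: "Baseline data will be collected at the time of enrollment and will consist of the enrollment form and the PHQ 9". The PFS baseline in the change test can therefore only be the week-one score.

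The documents contain no repeated-measures model, imputation, missing-data rule, analysis population or expected dropout. The analytic approach is to be guided by biostatistical support services.

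**The concern.** A t-test on change, a regression of the final score on the first, and ANOVA in its usual form all need the end-of-study score. A mother who answers at weeks one and six and is then lost contributes nothing, although her week-six score carries information about the missing value. Separate tests at each wave do not recover it.

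Two things are at stake. The first is bias. Week six is when the hybrid arm finishes its virtual course and home visits begin, so the arms differ in service format before that point and in visit frequency after it. Loss that differs by arm is plausible. If mothers doing poorly at week six leave one model more often, the completers flatter that model. The protocol intends these short-term results as leading indicators of longer-term ones, so this could affect which model looks preferable. The second is precision, where every mother counts among 30.

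**Working it through.** The plan states no effect size, SD, correlation or dropout figure for the PFS, so there is nothing of its own to reproduce. What follows is illustration.

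**Inputs.** From the protocol: n = 15 per arm and three waves. Assumed: PFS SD = 1 at each wave; correlations r12 = 0.5 (weeks one and six), r23 = 0.7 (week six and end) and r13 = 0.45 (week one and end); 25% lost after week six, so m = 0.75 × 15 = 11.25 completers per arm on average.

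**Precision, large-sample formulas.**
- End-of-study variance given week one: v3 = 1 − 0.45² = 0.7975.
- Share of v3 explained by week six: R² = (0.7 − 0.5 × 0.45)² / (0.75 × 0.7975) = 0.2256 / 0.5981 = 0.377.
- Change test in completers: 2(2 − 2·r13)/m = 2.2/11.25 = 0.196.
- Completer regression on week one: 2·v3/m = 1.595/11.25 = 0.142.
- Three-wave likelihood, adjusted for week one: 2·v3·[(1 − R²)/m + R²/n] = 1.595 × (0.623/11.25 + 0.377/15) = 0.128.

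Simulation at 15 per arm allows for the small sample. The SDs of the estimated difference are 0.446 (change test), 0.388 (completer regression) and 0.369 (three-wave). Then:
- Adjusting for week one: (0.388/0.446)² = 0.757, about 24% less variance.
- Adding week six: (0.369/0.388)² = 0.904, about a further 10%.
- Both steps: (0.369/0.446)² = 0.685, about 32%.

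With other assumed correlations (0.3 to 0.7, equal or decaying with time) and 3 or 5 of 15 lost per arm, week six lowers the variance by 1% to 11%.

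**The form of the model matters.** If all three waves are outcomes and the arm means at week one are left free, the SD is about 0.40 for the end-of-study difference and 0.41 for the difference in change. Both are worse than completer regression (0.388). The 0.369 needs week-one PFS as a covariate, or arm means held equal at week one.

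**Bias.** Suppose loss in the traditional arm is random at 25%. In the hybrid arm the log-odds of loss (25% at the mean) rise by a slope s per SD fall in week-six PFS. Let δ be the resulting upward shift in mean week-six score among hybrid completers. The true difference is zero.
- Change test: bias = (r23 − r12)·δ = 0.2δ.
- Completer regression: bias ≈ (r23 − r12·r13)·δ = 0.475δ.

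| s | δ | Change test | Completer regression |
|---|---|---|---|
| 0.5 | 0.125 | 0.025 | 0.06 |
| 1.0 | 0.242 | 0.05 | 0.11 |
| 1.5 | 0.340 | 0.07 | 0.16 |
| 2.0 | 0.418 | 0.08 | 0.20 |

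Simulation agrees: 0.03–0.08 SD for the change test and 0.06–0.21 SD for completer regression. The three-wave estimate stays within about 0.005 SD of zero.

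**Sensitivity.** If all correlations are 0.5, r23 − r12 = 0 and the change test is unbiased. With the lowest 10% to 30% of week-six scorers lost from one arm and random loss in the other, completer regression is then biased by 0.05 to 0.14 SD, and the three-wave model is again close to zero.

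**The case against.** The plan does not commit to a completer analysis. Its list of methods is open, advice is still to come, and the sentence after the change test gives all three waves a role. A reader might infer that week six is ignored altogether. The documents do not support that: week six is absent from the change test, and its role in comparing the models is left undefined. That mothers lost before the end are dropped follows from the usual form of the named methods and the lack of a missing-data rule; the plan does not say it.

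A reader might also take the whole reduction of about 32% as the price of leaving out week six. It is not. Most of it comes from adjusting for week one, and multiple regression, already on the list, can do that.

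The biases are small beside a standard error near 0.4 SD, and the larger ones need a steep slope in one arm only (odds of loss multiplied by 2.7 per SD at s = 1.0 and by 4.5 at s = 1.5). This is also a 30-mother pilot with no primary endpoint named.

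All of this limits the size of the point. What remains is that no method now in the plan keeps these mothers, and an analysis chosen after dropout is seen can be chosen to suit the result.

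**Conclusion.** The point holds in a moderate form. As written, the PFS change test has no place for week six, and under the named methods it would leave out mothers without a final score. The main reason to change is protection against selective loss: a bias of about 0.03–0.08 SD for the change test (none with equal correlations) or 0.06–0.21 SD for completer regression, against about zero for a three-wave likelihood model. Precision comes second, with about 10% less variance from week six (1–11% across the ranges tried).

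These sizes rest on assumed correlations, loss rates and strength of the loss mechanism. The near-zero bias holds only if loss depends on observed scores. Treating week one as baseline also assumes that the first week of services has not yet separated the arms. The point is worth acting on but not fatal to a pilot.

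**What to change.** State that the between-model PFS analysis is a mixed model for repeated measures, as follows:
- **Outcomes:** week-six and end-of-study PFS.
- **Terms:** model, time, model-by-time, week-one PFS and week-one PFS-by-time.
- **Covariance and degrees of freedom:** unstructured covariance, Kenward-Roger degrees of freedom.
- **Equivalent form:** all three waves as outcomes, with arm means constrained equal at week one.
- **Population:** every randomized mother with a week-one PFS and at least one later PFS (any PFS in the constrained form), analysed as randomized.
- **Main contrast:** the hybrid minus traditional difference at end of study.

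Name week one as the PFS baseline, and report the number lost by arm.

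The cost is a change of wording and slightly more analysis work, with no new data. The model relies on a missing-at-random assumption, which the plan should state.
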